### 2.2 Secondary Objectives

- 1) Investigate whether or not the intervention with low dose whole brain irradiation changes the recognized progression of Alzheimer's disease through cognitive testing.
- 2) To monitor quality of life parameters.

- 3) Collect information from AMYvid® PET Scans before and after treatment to investigate if there is any correlation between neurocognitive/quality of life scores and changes in amyloid plaque size, number and location.

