## **3.0 Methodology**

### ***3.1 Dose Levels and Sample Size Calculation***

In the context of this pilot study, traditional levels of  $\alpha$  (the Type I error rate) and  $\beta$  (the Type II error rate) are inappropriate since the objective of the research is not to provide definitive support for one treatment over another. In trials of safety such as this the objective is to show that the tested intervention produces a safety profile equal to a known standard therapy.

The nearest well-documented clinical situation to this novel study is the use of prophylactic cranial irradiation (PCI) in patients with limited disease small cell lung cancer (SCLC). Between September 1999 and December, 2005, 720 patients with limited-stage SCLC in complete remission after chemotherapy and thoracic radiotherapy from 157 centers in 22 countries were randomly assigned to a standard (n=360, 25 Gy in 10 daily fractions of 2.5 Gy) or higher PCI total dose (n=360, 36 Gy) delivered using either conventional (18 daily fractions of 2 Gy) or accelerated hyperfractionated (24 fractions in 16 days with two daily sessions of

1.5 Gy separated by a minimum interval of 6 hours) radiotherapy [54,55]. In this study 52% of patients experienced acute toxicity during PCI: headache in 85 patients in the 25 Gy group (24%) and 99 patients in the 36 Gy group (28%), respectively, fatigue in 106 (30%) and 121 (34%)

**Fig. 2** Upper limit of the  $100 \times (1 - \alpha)\%$  one-sided confidence interval for the true underlying adverse event rate,  $\pi$ , for increasing sample sizes when zero events of interests are observed

patients, insomnia in 14 (4%) and 13 (4%) patients, and nausea or vomiting in 80 (23%) and 101 patients (28%), with no significant differences between the two groups. Only two patients in the higher-dose group interrupted PCI because of acute toxicity: one because of grade 2 nausea or vomiting, and one because of scalp dermatitis. There were five serious adverse events, all of which occurred in the 25 Gy

group: one death (2 months after PCI) with undocumented neurological deterioration, one generalized seizure (12 months after PCI) treated with no sequelae, one transient ischemic attack (6 months after PCI), one bilateral cataract (29 months after PCI), and one death due to generalized seizure in a patient treated for epilepsy (29 days after PCI).

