As this is a pilot study comprising of two groups of 15 patients, the statistical assessment of endpoints will be descriptive and not inferential. This is a pilot study which is a requisite initial step in exploring an innovative application of radiation treatment and as such its goal is to inform feasibility and identify modifications needed in the design of a larger ensuing hypothesis testing study. In this study we are not testing hypotheses due to the limited state of knowledge about radiation treatment in this population of patients and the FDA-mandated sample size.

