### **3.10. Cognitive Assessment and Quality of Life Assessment During Treatment**

The Mini Mental Exam and ADAS-Cog are the two most commonly used tests of cognition in Alzheimer's Disease [58]. After treatment these tests will be administered by study designated, trained professional at 6 (+1) weeks, 3 (+1) months, 6 (+1) months and 12 months. Given that the ADAS-Cog is not used routinely in clinical practice (but rather a research assessment) and that the personnel involved may not necessarily be doing other studies requiring ADAS-Cog, it will not be possible to blind the professional doing the testing. The ADAS-Cog yields a single score that reflects the arbitrary weighting of performance in several cognitive domains including learning, language and spatial cognition but does not address executive function. A normal score for someone who does not have Alzheimer's or another type of dementia is 5; the greater

the dysfunction, the greater the score [59]. The properties of the ADAS-Cog are well understood; there is a curvilinear relationship between disease severity and rate of change on the ADAS-Cog. In a large clinical trial the baseline score for placebo-treated patients in the ADAS-Cog range of 13 to 26 was  $24.2 \pm 9.4$  and this increased to  $29.9 \pm 13.7$  representing a decline of  $5.7 \pm 8.2$  points over 1 year [60]. In this trial, a significant benefit in the active group was considered to be a 50% reduction in cognitive decline as indicated by change in ADAS-Cog score compared with the placebo group. In this study, patients who have an increase of no more than 50% (~3 points) on the ADAS-Cog at the end of treatment will be considered responders. This is equivalent to a delay in decline of about 6-8 months. Longitudinal analysis will be carried out for each individual patient using a fixed quadratic effect of time, dependent on the baseline level of ADAS-Cog, i.e., an interaction of baseline ADAS-Cog and the quadratic component of time.

The MMSE is a commonly used 30-point scale for assessing cognitive function in the domains of orientation, registration, attention and calculation, recall, language, and praxis. A MMSE score of 10 to 20 suggests moderate dementia. On average, the MMSE score of a person with moderate dementia declines about three to four points in a 12-month period. A similar analysis to that described above for the ADAS-Cog test will be carried out taking into account time and baseline MMSE score.

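### Section 3.10 turns a group-mean, placebo-referenced ADAS-Cog benchmark into an individual 3-point responder cut that about 37% of untreated patients would already meet, and names no cohort-level summary of change beside it

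*Combined protocol and SAP*

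**What the plan says.** Secondary objective 1 (section 2.2) asks whether low-dose whole brain irradiation "changes the recognized progression of Alzheimer's disease through cognitive testing". Section 2.4 defines the matching endpoint as change on MMSE and ADAS-Cog. It mentions neither responders nor a summary measure.

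The benchmark is in section 3.10. It cites placebo patients in a large trial, "representing a decline of $5.7 \pm 8.2$ points over 1 year", and reports that in that trial "a significant benefit in the active group was considered to be a 50% reduction in cognitive decline as indicated by change in ADAS-Cog score", the comparison being with placebo. It then defines an individual response: "patients who have an increase of no more than 50% (~3 points) on the ADAS-Cog at the end of treatment will be considered responders". It equates this with a delay in decline of about 6 to 8 months.

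The same paragraph plans a full-scale analysis: "Longitudinal analysis will be carried out for each individual patient", with a quadratic time effect and an interaction between baseline ADAS-Cog and the quadratic term. A similar analysis is planned for MMSE, which has no responder cut but a quoted decline of three to four points in 12 months.

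Section 3.1 sets the frame: "two groups of 15 patients", one per dose, and "the statistical assessment of endpoints will be descriptive and not inferential".

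**The concern.** Halving a group's mean decline describes an average. It does not follow that a patient whose score rises by 3 points or less has responded. With an SD of 8.2 around a mean of 5.7, many patients stay under 3 points with no treatment effect at all. The cut also treats a 4-point and a 20-point rise alike, and a 2.9-point rise like a 10-point improvement.

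No other numerical benefit threshold is attached to objective 1. Section 3.5 gives general thresholds for meaningful change (4 on MMSE, 7 on ADAS-Cog), and the cognitive items in section 3.12 are deterioration rules. The trial has no concurrent control, and section 3.10 says the tester cannot be blinded. A result such as 6 responders out of 15 could therefore be read as benefit when about that number is expected with no effect. Section 3.1 also says the pilot is meant to inform a larger study, and a responder count does not supply the mean and SD of change that such a study would be planned on.

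**Working it through.** **Inputs.** From section 3.10: placebo change +5.7, SD 8.2, over 1 year; cut about 3 points. From section 3.1: n = 15 per dose. The shape of the distribution is an assumption, because the documents give none.

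**The plan's own figures.**
- Half of the quoted decline: 0.5 × 5.7 = 2.85, which rounds to 3. So 5.7 is the base of the 50%.
- Delay: 2.85/5.7 × 12 = 6.0 months, and 3/5.7 × 12 = 6.3 months. This agrees with the lower end of 6 to 8 months, and it too is a conversion of an average.

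**Expected responder share (normal change, 12 months).**
- No effect: Φ((3 − 5.7)/8.2) = Φ(−0.329) = 0.371; 15 × 0.371 = 5.6 patients.
- Decline halved: Φ((3 − 2.85)/8.2) = Φ(0.018) = 0.507; 15 × 0.507 = 7.6 patients.

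The full benchmark effect moves the expected count by 2 patients. With no effect, the binomial chance of 7 or more responders in 15 is 30%.

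**Information in the share relative to the mean.** The large-sample relative efficiency is f(c)² × SD² / [p(1 − p)], where f is the density at the cut c and p the share below it. For the normal this is φ(−0.329)² / (0.371 × 0.629) = 0.3779² / 0.2333 = 0.612. Fifteen dichotomised patients then carry the information of 15 × 0.612 = 9.2. For an assumed SD of 6 to 10 the efficiency is 0.59 to 0.62.

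**Sensitivity to shape.** Mean and SD are held and only the shape is changed. The t distributions are rescaled to SD 8.2. The gamma has shape 4 and scale 4.1, so skewness 1, and is shifted to the stated mean.

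| Shape | Share, mean 5.7 | Share, mean 2.85 | Efficiency, mean 5.7 | Efficiency, mean 2.85 |
|---|---|---|---|---|
| Normal | 37% (5.6 of 15) | 51% (7.6) | 0.61 | 0.64 |
| t, 8 df | 36% (5.4) | 51% (7.6) | 0.74 | 0.80 |
| t, 5 df | 34% (5.2) | 51% (7.6) | 0.86 | 0.96 |
| Gamma, skewness 1 | 43% (6.4) | 57% (8.6) | 0.79 | 0.61 |

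The untreated share is fairly stable, at 34% to 43%. The efficiency loss is not: at mean 5.7 it runs from 39% under normality down to 14%.

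**Precision at n = 15.** The 95% half-width for the mean is 2.145 × 8.2/√15 = 4.5 points. The exact 95% interval for 6 of 15 responders is 16% to 68%, which covers both 37% and 51%.

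**Time point.** The responder sentence refers to the end of treatment. The study calendar (section 6.0) has no ADAS-Cog then: after baseline the tests are at 6 weeks and 3, 6 and 12 months. The 5.7-point benchmark is a 1-year change, so the shares above assume the 12-month visit.

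**The longitudinal model.** Each patient has five scheduled assessments and one baseline score. Baseline is constant within a patient, so its interaction with quadratic time cannot be separated from the quadratic term in a single-patient fit. It can be estimated only across patients.

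**The case against.** The strongest reply is that nothing is lost. Section 2.4 defines the endpoint as change, the full-scale scores are analysed longitudinally, and the baseline interaction makes sense only in a pooled model, so a group-level full-scale analysis is arguably already intended. No required responder count or decision hangs on the cut, and section 2.2 does not mention it. This stands in large part. A reader might infer that the plan throws away about 39% of its cognitive information, or that the responder call is its only way to read cognitive benefit. The documents support neither. The 39% applies to the responder share alone and depends on normality. What remains is that the longitudinal analysis is worded as a per-patient fit and has no cohort summary or benchmark.

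A reader might also cast the point as lost power. Section 3.1 says that traditional error rates "are inappropriate since the objective of the research is not to provide definitive support for one treatment over another", and no test is planned, so the loss is one of descriptive precision.

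The mean also has weaknesses. Its half-width of 4.5 points exceeds the 2.85-point gap of interest. The benchmark comes from placebo patients in an ADAS-Cog range of 13 to 26, whereas this trial enrols MMSE 10 to 20, and section 3.10 itself says the rate of change depends on severity. A 12-month mean also needs 12-month scores. In the instrument paper reproduced in the appendices (Table 1), patients with MMSE 10 to 15 fell from 45 to 29 with valid word-list data at 12 months. All of this stands as caution in reading the mean. It does not favour the cut, which uses the same benchmark and the same visit.

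**Conclusion.** The concern holds in a limited form. Section 3.10 does convert a placebo-referenced group benchmark into an individual cut, and that cut is the only numerical benefit threshold stated for secondary objective 1. On the plan's own mean and SD, and assuming normal 12-month change, about 37% of untreated patients would meet it, against 51% if decline were halved. The share carries roughly 60% of the information in the mean under normality, and 74% to 86% at the no-effect mean under the other shapes tried.

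The more robust part of the finding is the high untreated share in a trial without a concurrent control; the exact efficiency figure is less secure. The primary safety objective is untouched. The change is worth making because it is cheap, reduces the risk that a responder count is misread as benefit, and gives the later study what it needs.

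**What to change.** In section 3.10:
- Name mean change in ADAS-Cog from baseline to 12 months in each dose cohort, with its 95% CI, as the main descriptive summary for secondary objective 1. Show the median and range beside it.
- Read it cautiously against the quoted 5.7 points and the halved 2.85 points, and say that the benchmark population differs in severity.
- Report MMSE in the same way against three to four points a year.
- Keep the 3-point responder share as supportive only, reported at the 12-month visit beside the roughly 37% expected with no effect.
- Reword the longitudinal analysis as a model pooled across patients.

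The cost is a few sentences and an extra table row per cohort, with no new visits or data. The downsides are that a mean of 15 is sensitive to extreme scores and to missing 12-month scores, so the number contributing should be shown, and that a half-width of about 4.5 points will not settle whether progression has changed.

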### **2.4 Secondary Endpoints**

- 1) Neurocognitive testing will be used to assess changes in cognitive function using the MMSE and ADAS-Cog. The tests will be administered by an appointed, trained site professional at baseline and at 6 weeks, 3 months, 6 months, and 12 months during follow-up.
- 2) Quality of life will be monitored via questionnaires completed by the patient prior to the start of irradiation and at 6 weeks, 3 months, 6 months, and 12 months during follow-up. Specific questionnaires include the QOL-AD and QUALID, which have been established as sensitive measures of various parameters of quality of life.
- 3) A pretreatment and post treatment (4 months) Amyvid PET/CT scan will be carried out to determine if there are any correlations between neurocognitive /QOL test results and amyloid number, size and location and changes after treatment.

[figure not shown]

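### The ADAS-Cog longitudinal model is specified patient by patient, where its baseline by time-squared interaction cannot carry information on baseline; it should be one model fitted across patients

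*Combined protocol and SAP*

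**What the plan says.** Section 3.10 gives the only longitudinal cognitive model in the documents: "Longitudinal analysis will be carried out for each individual patient using a fixed quadratic effect of time, dependent on the baseline level of ADAS-Cog". It then spells out the dependence as "an interaction of baseline ADAS-Cog and the quadratic component of time". A little earlier it offers background on the scale: "there is a curvilinear relationship between disease severity and rate of change on the ADAS-Cog". For the other instrument it says: "A similar analysis to that described above for the ADAS-Cog test will be carried out taking into account time and baseline MMSE score".

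Section 2.4 and the calendar in section 6.0 schedule five cognitive assessments per patient: baseline, 6 weeks, and 3, 6 and 12 months. Section 2.2 asks whether the intervention "changes the recognized progression of Alzheimer's disease through cognitive testing", and section 2.4 states the endpoint as "Neurocognitive testing will be used to assess changes in cognitive function using the MMSE and ADAS-Cog". Section 3.1 says that endpoints are assessed descriptively, in two groups of 15. No section mentions a mixed model, random effects, or a second-stage regression that combines patients.

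**The concern.** An interaction with baseline describes how the course over time differs between patients who start at different levels. That needs variation in baseline. Inside one patient's data there is none, so a model fitted separately to each patient cannot do what its own interaction term implies.

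An analyst who follows the text literally meets one of two outcomes. The software may drop a term or report a singular fit. Otherwise it returns a coefficient that looks like a baseline effect but is only a rescaled curvature. Tabulated by patient, such coefficients would mislead, because two patients with the same decline would differ only through their baselines. Separate fits also do not directly give a summary of the cohort's course, which is what the first secondary objective concerns.

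**Working it through.** **Plan's own figure.** The plan states no figure for this model, so there is none to reproduce. Its only design figures are the zero-event limits in section 3.1 (for example 1 − 0.05^(1/15) = 18.1%, as stated). They do not depend on it.

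**Inputs.** Assessment times t = 0, 1.5, 3, 6 and 12 months (sections 2.4 and 6.0, taking 6 weeks as 1.5 months); one baseline b per patient; 15 patients per cohort (section 3.1). For illustration b = 24.2, the mean that section 3.10 cites; the algebra holds for any non-zero b.

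**Version 1: time-squared and the interaction both entered, one patient.** Columns are 1, t, t² and b·t².

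| t | t² | b·t² (b = 24.2) |
|---|---|---|
| 0 | 0 | 0 |
| 1.5 | 2.25 | 54.45 |
| 3 | 9 | 217.8 |
| 6 | 36 | 871.2 |
| 12 | 144 | 3484.8 |

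The last column is 24.2 times the one before it in every row. The rank is 3 of 4, so the two coefficients cannot be separated.

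**Version 2: the interaction replaces time-squared, one patient.** Columns are 1, t and b·t², rank 3 of 3, so the fit runs. Since b is constant, γ·b·t² = β·t² with γ = β/b. Fitted values equal those of the plain quadratic.

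Take an assumed course of changes 0, 0.5, 1.2, 2.6 and 5.7 points at the five times. The values are illustrative; only the end value matches the one-year decline cited in section 3.10. The plain quadratic gives β = 0.00722 per month², whatever the baseline. The interaction coefficient is then:

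- b = 15: 0.00722/15 = 0.00048
- b = 20: 0.00722/20 = 0.00036
- b = 30: 0.00722/30 = 0.00024

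That is a twofold spread (30/15) for one and the same decline. The fitted values agree with the plain quadratic to within rounding error (differences below 1e-12).

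Each such fit leaves 5 − 3 = 2 residual degrees of freedom, or 4 − 3 = 1 if only post-baseline scores are responses.

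**Across patients.** Baseline now varies between rows, so b·t² is no longer a multiple of t².

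- 15 patients × 5 scores = 75 rows, columns 1, t, t², b·t²: rank 4 of 4.
- 15 patients × 4 post-baseline scores = 60 rows, columns 1, b, t, t², b·t²: rank 5 of 5.
- 30 patients × 4 post-baseline scores = 120 rows, the same columns plus a dose indicator: rank 6 of 6.

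The interaction is estimable in each design. Its precision is not computed here: that would need the residual variance and within-patient correlation over the visits, and the documents do not give the correlation.

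**The case against.** The strongest reply is that a model across patients was meant all along. A fixed effect of time with a baseline interaction is ordinary repeated-measures language, and the per-patient phrase may only signal that each patient contributes repeated scores. That is probably right. But such a model is fitted across patients, and the sentence says the reverse. If it was intended, the edit only makes it explicit.

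Other readings do not rescue the text. Per-patient quadratics followed by a regression of their coefficients on baseline would work. With complete data they give the same estimate as least squares with baseline interacting with every time term. But that second stage is across patients and is not stated. A curve fixed in advance by baseline, against which each patient is judged, is also conceivable, but the plan gives no such curve or coefficients, and the dependence would then be assumed rather than shown.

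It is also fair to say that patient-level description suits this trial. The responder rule ("patients who have an increase of no more than 50% (~3 points) on the ADAS-Cog at the end of treatment will be considered responders") and two of the stopping rules in section 3.12 classify or count individuals. A plain quadratic per patient is a valid description, and no section plans a table of raw interaction coefficients. This limits the harm without making the interaction meaningful.

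A reader might infer that the trial sets out to estimate dependence on baseline and will fail at it. No objective or endpoint lists that aim. The remark on severity and rate of change is background, and the defect is that the model as worded cannot support its own term. A reader might also infer that the cognitive endpoint as a whole cannot be analysed. It can: a mean 12-month change per cohort can still be reported.

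**Conclusion.** The point holds as a defect of specification: the sentence as written describes a model that is either not identifiable or a rescaled plain quadratic. This is algebra. It rests only on each patient having a single baseline value and assumes no variance. The twofold spread in coefficients illustrates the rescaling and does not predict a result.

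What the authors intended is less certain than the algebra; a model across patients is the likely intent. MMSE is affected only because its analysis is defined by similarity to this one.

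The consequence is limited to a secondary, descriptive analysis. It would be wrong to extend the point to the primary safety endpoint, the rationale for 15 patients per cohort, the responder rule or the stopping rules, none of which uses this model. Nor does the correction promise a more precise mean change. With 15 patients any estimate of dependence on baseline will be imprecise and purely descriptive. The change should be made because the text is wrong as it stands and the repair costs little.

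**What to change.** In section 3.10, replace the wording that makes the individual patient the unit of the fit. Specify one repeated-measures model fitted across patients that accounts for within-patient correlation and contains time, time-squared and baseline by time-squared.

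- **Role of baseline.** State it. If baseline is a covariate, model only the four post-baseline scores and add a baseline main effect. That main effect is an addition to the terms that the plan names.
- **Cohorts.** Fit the model by dose cohort, or over all 30 patients with a dose term. Both are estimable. The separate assessment of the second cohort in section 3.1 follows text on safety and only weakly favours the first option, so the choice should be stated.
- **MMSE.** Say that the model has the same form, with baseline MMSE.
- **Individual patients.** Show trajectories as plots rather than as tables of per-patient interaction coefficients.

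The cost is a rewritten sentence or two and slightly more analysis work. No new data, visits or patients are needed.

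### The ADAS-Cog model names only a baseline × time² interaction, which forces one initial slope on all patients, depends on an unstated time origin and cannot be estimated patient by patient

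*Combined protocol and SAP*

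**What the plan says.** Section 3.10 gives the reason for letting baseline into the model: "there is a curvilinear relationship between disease severity and rate of change on the ADAS-Cog". It then sets out the analysis. "Longitudinal analysis will be carried out for each individual patient", it says, "using a fixed quadratic effect of time, dependent on the baseline level of ADAS-Cog", and a clause introduced by i.e. defines this as "an interaction of baseline ADAS-Cog and the quadratic component of time". No baseline × linear-time term is named. The section does not say whether baseline also enters as a main effect, whether the outcome is the score or its change, where time zero lies, or what the random effects are. The MMSE is to be handled in like manner.

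Tests are given before treatment and then at "6 (+1) weeks, 3 (+1) months, 6 (+1) months and 12 months". On size and status, section 3.1 states that "this is a pilot study comprising of two groups of 15 patients" and that "the statistical assessment of endpoints will be descriptive and not inferential".

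**The concern.** The rationale and the model do not match. The rationale is that the rate of decline varies with severity, and that this relation is curved in severity. The model puts the curvature on time instead and lets baseline act only through time squared. Two patients of very different severity must then start to decline at the same rate and can separate only in proportion to t². A quadratic interaction without its linear counterpart also gives a different fit when the time origin moves.

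This is the only trajectory analysis in the plan, it serves the first secondary objective (section 2.2), and the MMSE inherits it. What is at stake is how the pilot describes the dependence of decline on severity at the 3- and 6-month visits, which a larger study might use.

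**Working it through.** **Inputs.** From section 3.10: post-treatment visits at 6 weeks (1.38 months), 3, 6 and 12 months; placebo ADAS-Cog in the large trial cited there, 24.2 (SD 9.4) at baseline, 29.9 (SD 13.7) at one year, change 5.7 (SD 8.2). From section 3.1: 15 patients per cohort.

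**1. The plan's own figure.** 29.9 − 24.2 = 5.7, and half of that is 2.85, the plan's threshold of about 3 points. It reproduces. The plan gives no figure for the longitudinal model itself.

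**2. Structure.** With B for baseline, the literal curve is b0 + b1·t + (b2 + b3·B)·t². Its slope is b1 + 2(b2 + b3·B)·t, which at t = 0 equals b1 for every B.

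**3. Fitted to one patient.** There are five observations and the columns 1, t, t² and B·t². B is a constant, so the fourth column is a multiple of the third: rank 3 of 4. The interaction cannot be estimated.

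**4. Fitted across patients, with a true severity effect linear in time.** Take the true between-patient difference as proportional to t.

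- No baseline main effect. Least squares of t on t² gives Σt³/Σt⁴ = 1973.6/22116.6 = 0.0892. Fitted over true is 0.0892·t: 0.27, 0.54 and 1.07 at 3, 6 and 12 months. Allowing for exchangeable within-patient correlation of 0.5 to 0.9, the 3- and 6-month ratios are 0.21–0.23 and 0.42–0.45.
- Baseline main effect, post-baseline visits only. The fit is 2.272 + 0.0696·t². At 3 months 2.899/3 = 0.97; at 6 months 4.779/6 = 0.80; at 12 months 12.30/12 = 1.02. The fit also implies a difference at time zero of 2.272/12 = 19% of the 12-month value, where there is none.
- Baseline main effect, baseline visit included. The fit is 1.594 + 0.0755·t², with ratios 0.76, 0.72 and 1.04.
- If half of the 12-month effect is linear and half quadratic, the ratios without a main effect are 0.41 and 0.69. If it is all quadratic, they are 1.

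**5. Time origin.** Keep the main effect and post-baseline visits, but measure time from 6 months. The fit becomes 2.939 + 0.160·(t − 6)², so at 6 months 2.939/6 = 0.49 instead of 0.80. With baseline and baseline × time, moving the origin changes nothing.

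**6. In points.** If the three SDs come from the same patients, the covariance of baseline and change is (13.7² − 9.4² − 8.2²)/2 = (187.69 − 88.36 − 67.24)/2 = 16.05. The slope is 16.05/88.36 = 0.18 points of 12-month decline per baseline point. Between patients 1 SD above and 1 SD below the mean (18.8 points apart) that is 3.41 points. Applying the ratios in step 4:

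| Difference (points) | 3 mo | 6 mo | 12 mo |
|---|---|---|---|
| True, if linear | 0.85 | 1.71 | 3.41 |
| Baseline × t², no main effect | 0.23 | 0.91 | 3.66 |
| With main effect, post-baseline visits | 0.82 | 1.36 | 3.50 |
| With main effect, baseline visit included | 0.65 | 1.23 | 3.55 |

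The 0.18 is fragile: a follow-up SD of 13.0 gives 0.08, and 12.5 gives 0.00.

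**7. Precision.** The implied correlation of baseline with change is 16.05/(9.4 × 8.2) = 0.21, so the residual SD is 8.2 × √(1 − 0.21²) = 8.0. With 15 patients the SE of the slope is 8.0/(9.4 × √14) = 0.23, and of the 12-month difference 18.8 × 0.23 = 4.3 points.

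**8. The average patient.** Time and time squared are both free. In 4000 simulated cohorts of 15 the mean fit at average baseline was 1.42, 2.84 and 5.67 points at 3, 6 and 12 months, with the plan's interaction alone and with both interactions alike (truth 1.43, 2.85, 5.70).

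**The case against.** Five arguments carry weight.

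- The large shortfall needs both a mainly linear true effect and no baseline main effect. The documents state neither. The word curvilinear in section 3.10 describes rate against severity, not score against time. This stands, and it is why the size can only be given as a range.
- The phrase "using a fixed quadratic effect of time, dependent on the baseline level of ADAS-Cog" could mean that the whole curve depends on baseline. The i.e. clause says otherwise. If the wider meaning was intended, the same rewrite is needed.
- Fitted patient by patient as written, no bias can arise because nothing is estimated. True, but a term that cannot be estimated is itself a defect.
- A sparse model is defensible with 15 patients. In simulation (85% of the residual SD as patient-level slopes, the rest visit noise), root mean squared error for the between-patient difference without a main effect was 0.70 and 1.46 points at 3 and 6 months with baseline × time² alone, against 1.73 and 2.75 with both interactions. So adding the linear term beside the quadratic one costs precision. Replacing one by the other adds no parameter. With a baseline main effect in both models the errors are equal at 3 months, 2.4 (linear) against 2.0 (quadratic) at 6, and 4.6 against 4.7 at 12.
- The consequence is limited. The responder rule, "patients who have an increase of no more than 50% (~3 points) on the ADAS-Cog", and the stopping rules in section 3.12 are framed as changes in test scores, not as fitted values from this model.

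A reader might infer that the fitted mean time course, or a comparison with expected decline at 3 and 6 months, is also distorted. The documents do not support that: the average-baseline curve is unaffected, and section 3.10 gives expected decline over one year only.

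**Conclusion.** The model sentence does not do what its rationale asks. It fixes a common initial slope, depends on an unstated time origin, and cannot be estimated if applied to each patient. These three statements follow from the wording alone.

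The numerical effect is conditional. For a severity effect linear in time, the fitted between-patient difference is 27% and 54% of the truth at 3 and 6 months without a baseline main effect, and 72–97% with one; it is 100% if the true effect is purely quadratic. It would be tempting to conclude that severity-related decline at the early visits will be fitted far too small. That is not established, because the documents fix neither the time course of the effect nor the presence of the main effect. On the cited SDs, the 12-month difference of about 3.4 points has an SE larger than itself, so in any one cohort sampling noise will outweigh the bias. No sample size, error rate or decision changes. The point is worth correcting before analysis because the analysis serves a stated secondary objective and the repair is cheap.

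**What to change.** Replace the sentence in section 3.10 with one mixed model fitted across patients, not to each patient separately. The outcome is the post-baseline score (or change from baseline); the fixed terms are time, time squared, baseline and baseline × time. State the time origin and the random effects. Baseline × time thus replaces baseline × time² as the primary interaction. Keep baseline × time², or baseline squared × time (which is closer to the stated rationale), only as a sensitivity term. Use the same form for the MMSE.

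The cost is wording. The swap itself adds no interaction parameter, although stating a baseline main effect adds one term if none was intended. The downside is imprecision: with 15 patients per cohort the SE is about 4 to 5 points on a 3.4-point 12-month difference (cited SDs, assumed to come from the same patients). Fitting both interactions together costs further precision at 3 and 6 months. Report the interaction with its interval, as description.
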